9.8 Concomitant Medications

All concomitant medications at the time of study entry will be identified through a medical chart review and recorded in REDCap. Participation in the study intervention must not impact use of concomitant medications at any stage of the study period.

10.0 EVALUATION DURING TREATMENT/INTERVENTION

All evaluations being conducted during the study intervention, including the window of time in which conduct of these tests is required, are described in the schedule of activities (Table 2). Further details are provided within this section. Assessments which are initially completed at baseline, midpoint and follow up may be repeated at the investigators discretion.

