6.1 CRITERIA FOR SUBJECT ELIGIBILITY

6.2 Subject Inclusion Criteria

- Aged 45–80 years
- Female
- Has been diagnosed with early-stage breast cancer
- Post-menopausal, defined as:
 - Age ≥ 45 with no menses for at least 2 years
 - Chemically induced menopause through ovarian suppression, as determined by the primary oncologist
- An interval of at least one year, but no more than five years, following the full completion of primary therapy for malignant disease. Primary therapy is defined as:
 - Surgery plus radiation
 - Surgery plus chemotherapy
 - Surgery plus trastuzumab
 - Surgery plus hormone therapy

Note: For patients who receive hormone therapy following surgery, the definition of one-year post-completion of therapy is defined by the surgery date. Patients who are currently receiving hormone therapy are eligible for enrollment.

- Weight of <205 kgs
- ECOG status of 0 or 1
- Life expectancy \geq 6 months
- Performing less than 150 minutes of structured moderate-intensity or strenuous intensity exercise per week.
- Exercise intolerance, defined by a VO_{2peak} below that predicted for active age- and sex-matched individuals (**see Appendix H**).
- Willing to be randomized to one of the study arms
- Able to complete an acceptable baseline CPET, in the absence of high risk ECG findings or other inappropriate response to exercise as determined by the investigator.
- Able to achieve an acceptable peak baseline CPET, as defined by any of the following criteria:
 - Achieving a plateau in oxygen consumption, concurrent with an increase in power output;
 - A respiratory exchange ratio \geq 1.10;
 - Attainment of maximal predicted heart rate (HR_{max}) (i.e., within 10 bpm of age-predicted HR_{max} [$HR_{max} = 220 - \text{Age}[\text{years}]$]);
 - Volitional exhaustion, as measured by a rating of perceived exertion (RPE) \geq 18 on the BORG scale (**see Appendix E**)

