7.1 Blinding

This study is open label. Due to the nature of aerobic training interventions, participants, exercise physiologists, investigators and Ex-Onc research staff cannot be blinded to arm allocation.

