Resting left ventricular function by 3-dimensional echocardiography (3DE)	
Three-dimensional transthoracic echocardiograms will be performed by experienced sonographers and acquired with commercially available equipment (Vivid 7 or E9, GE Healthcare, Milwaukee, WI).
 
Following completion of the 2DE, a full volume dataset will be acquired using a matrix array transducer with gated 4 beat acquisitions for assessments of left ventricular (LV) volumes by 3DE. A 3DE acquisition of the entire LV will be generally performed in <10 seconds. All assessments will be stored digitally for offline analyses performed using EchoPAC PC workstation (version BT11, GE Medical, Milwaukee, WI).
 
Conventional 2D measurements of LV dimensions, Doppler, and diastolic function parameters will be performed and averaged over 3 cardiac cycles according to American Society of Echocardiography guidelines.²⁹⁻³¹
 
Left ventricular volumes and left ventricular ejection fraction (LVEF) by 3DE will be determined by manipulating the full volume dataset to derive conventional apical 4-, 3-, and 2-chamber views using TomTec offline analysis software (4D LV-Function, Unterschleisheim, Germany). After selection of reference points, a 3D endocardial contour will be automatically generated and manual adjustment will be performed as necessary. The resultant end-diastolic (EDV) and end-systolic volumes (ESV) will be used to calculate LVEF.³²

Symptom-limited CPET to assess peak oxygen consumption (VO_{2peak})	
VO_{2peak} will be evaluated using an electronic motorized treadmill test with 12-lead ECG monitoring (Mac® 5000, GE Healthcare) performed by certified exercise physiologists.
 
CPET provides assessment of peak oxygen consumption (VO_{2peak}). Expired gases will be analyzed continuously by a metabolic measurement system (Parvo Medics TrueOne 2400).
 
During the test, participants will begin walking on a treadmill at a participant-specific designated speed and grade for approximately 2 minutes. The speed and/or grade will then be increased every 1–2 minutes until exhaustion or a symptom-limitation is reached.
 
During exercise, oxyhemoglobin saturation will be monitored using finger pulse oximetry, while blood pressure will be measured manually by auscultatory sphygmomanometer every two minutes (± 1 minute).

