10.3 Exercise Contamination

We will monitor the amount of exercise performed outside of the study in all study arms using subjective methods. Participants in all arms will be asked to complete the GLTEQ at midpoint and at study follow-up to report all exercise behavior performed outside the context of the exercise prescribed in the trial. This questionnaire is important to assess the degree of exercise being performed outside of the structured sessions in all arms, which may potentially contaminate study results. At the midpoint assessment, participants will be asked to report the average weekly exercise performed outside of study aerobic training sessions since study enrollment. At the follow-up visit, participants will be asked to report the average weekly exercise performed outside of study aerobic training sessions over the past 8 weeks since the midpoint assessment.

At the investigators discretion, patients may be required to repeat any of the above assessments.

Table 2. Schedule of Activities

Study Period or Visit Study Week Window (Weeks)	Training begins at Week 1 Treatment Period (16 weeks)						Training ends at Week 17
	Screening	Baseline	Pre-Treatment	Monthly Follow-up	Midpoint Assessment	Monthly Follow-up	Study FU
	NA	-30 days ¹	-2 to -1	4	8	12	17
	NA	NA	±1	±1	±1	±1	±2
General Activities¹							
Informed Consent		X					
Medical History	X						
Height, Weight, BMI	X	X					X
Vital Signs	X						X
Performance Status (ECOG) ²	X						
Concomitant Medications	X						
Randomization ³			X				
Study-Related End Points							
Cardiopulmonary exercise test (CPET) ⁴		X			X ⁵		X
Resting 3D Echocardiogram		X					X
Post-exercise 2D Echocardiogram		X					X
Pulmonary function		X					X
Body composition (DEXA)		X					X
Regional arterial stiffness		X					X
Flow-mediated dilatation (FMD)		X					X
Godin Leisure-Time Exercise Questionnaire (GLTEQ)		X			X		X
Patient-reported outcomes (Lifestyle Questionnaire)		X					X
Complete Blood Count (CBC)		X		X	X	X	X
Lipid Panel & Fasting Glucose		X					X
Aerobic Training ⁶				X	X	X	
Research Blood draw		X		X	X	X	X

- [1] Testing slots/procedures availability must be taken into consideration when scheduling study follow-up visits. Visits may be split across the window to permit for completion of all study-related assessments.
- [2] Performance status by Eastern Cooperative Oncology Group (ECOG) scoring.
- [3] Randomization should be performed on or up to 2 weeks prior to Day 1, but only after eligibility is confirmed.

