12.1 CRITERIA FOR THERAPEUTIC RESPONSE/OUTCOME ASSESSMENT

12.1 Primary Study End Point

Exercise Capacity (VO_{2peak}): As described in Table 1, VO_{2peak} will be evaluated using an electronic motorized treadmill CPET test with 12-lead ECG monitoring (Mac ® 5000, GE Healthcare).

Due to the presence of significant, and potentially clinically important, variability in CPET procedures (VO_{2peak} measurement), all potential participants will perform a second CPET at baseline to account for potential learning effects and variability.³⁵ If both the first and second CPET achieve acceptable test criteria, results of the second test will be used in all protocol procedures and statistical analyses.

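### Unblinded investigators may repeat the Week 17 CPET at will, and the plan does not say which Week 17 VO2peak value is analysed

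*Combined protocol and SAP*

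**What the plan says.** The permission to repeat tests appears twice. Section 10.0 says: "Assessments which are initially completed at baseline, midpoint and follow up may be repeated at the investigators discretion". Section 10.3, just before the schedule of activities (Table 2), says: "At the investigators discretion, patients may be required to repeat any of the above assessments". Neither sets a trigger, limits the number of repeats or asks for the reason to be recorded. Table 2 places the follow-up CPET at Week 17 with a window of plus or minus 2 weeks, so there is time for a second test.

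On blinding, section 7.1 says that "participants, exercise physiologists, investigators and Ex-Onc research staff cannot be blinded to arm allocation". Table 1 in section 8.2 describes the CPET as "performed by certified exercise physiologists", so the testers belong to an unblinded group.

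The only rule on which test counts is in section 12.1. Its reason is given as "Due to the presence of significant, and potentially clinically important, variability in CPET procedures", and its scope is the planned baseline pair: "all potential participants will perform a second CPET at baseline to account for potential learning effects and variability". If both of those tests are acceptable, "results of the second test will be used in all protocol procedures and statistical analyses". The criteria for an acceptable test are in section 6.2, as an eligibility condition: "Able to achieve an acceptable peak baseline CPET, as defined by any of the following criteria". Section 14.3 specifies a regression of VO2peak from baseline to Week 17 and does not mention more than one Week 17 value.

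**The concern.** At baseline the plan handles CPET variability with a fixed rule. Randomisation follows the baseline assessments (end of section 8.2), so baseline repeats cannot be chosen by arm. At Week 17 the arm is known, and the rule is replaced by discretion.

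A low value that is retested tends to rise by regression to the mean, even with no change in fitness. Keeping the better of two tests raises it further. If low values were retested more often in one arm, the comparison of arms on the primary endpoint would shift for reasons unrelated to training. Because blinding is not feasible here, an objective retest rule is one of the few protections available, and the plan has none at the visit that matters.

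**Working it through.** **1. The plan's own figure.** Section 14.2 gives a 2.5 mL/kg/min difference between A and B, SD of change 4.0, 58 per arm and two-sided alpha 0.025. The standard error is 4.0 × √(2/58) = 0.743. Power is 86.2% by the noncentral t and 87.0% by the normal approximation, which matches the stated 86%. A retest rule does not alter this figure.

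**2. Who the clause can reach.** Section 1.0 reports 39 participants already randomised to Arm B at Duke and plans 19 more at MSK (39 + 19 = 58). Section 16.2 says those on trial at Duke completed their procedures. Whether the Duke protocol had the same clause cannot be seen. If it did not, the clause reaches 19/58 = 33% of Arm B.

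**3. Size of a possible shift.** Assumptions not in the documents:
- The within-person test-retest SD, s, is 1.0 to 2.0 mL/kg/min.
- The lowest fraction f of observed changes in Arm B is retested, and nobody in the other arms.
- A retest brings no practice gain.

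If the second test replaces the first, the rise in the arm mean is s² × φ(z_f) / 4.0, where z_f is the normal quantile for f and φ the normal density. For f = 10% and s = 1.0 this is 1 × 0.1755 / 4.0 = 0.044. For f = 50% and s = 2.0 it is 4 × 0.3989 / 4.0 = 0.399. The case where the better test is kept was simulated with 2 million draws per setting. Multiplying by 19/58 gives the MSK-only figures.

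| Lowest share of Arm B retested | Second counts, all 58 | Better counts, all 58 | Second counts, 19 at MSK | Better counts, 19 at MSK |
|---|---|---|---|---|
| 10% | 0.04–0.18 | 0.08–0.22 | 0.01–0.06 | 0.03–0.07 |
| 20% | 0.07–0.28 | 0.15–0.38 | 0.02–0.09 | 0.05–0.12 |
| 50% | 0.10–0.40 | 0.33–0.76 | 0.03–0.13 | 0.11–0.25 |

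Each range runs from s = 1.0 to s = 2.0, in mL/kg/min.

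**4. Scale.** The MSK-only range runs from 0.014/2.5 = 0.6% to 0.25/2.5 = 10% of the target difference. Against the standard error of 0.743, a shift of 0.25 moves the two-sided type I error from 0.025 to about 0.033, and a shift of 0.09 moves it to about 0.026. The largest all-58 value, 0.76, would give about 0.113.

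**5. Equal retesting.** If the same share of low values were retested in both arms at MSK (20 in A, 19 in B), even the most extreme setting would leave a net shift of only 0.76 × (20 − 19)/58 = 0.013.

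**The case against.** The strongest reply concerns size and direction, and most of it stands. About two thirds of Arm B was randomised before this protocol, so on the visible text the clause can affect only 19 of 58. The discretion applies to every arm alike, and even-handed use would leave A minus B essentially where it was. The largest figures need half of one arm retested, no one elsewhere, the better result kept and the highest assumed SD. Nothing in the documents supports that combination.

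A reader might infer that the bias must favour nonlinear training, because Arm B is expected to gain most. That follows only from assuming that Arm B alone is retested. A reader might also infer that a disappointing Week 17 value is always replaced by its repeat. Section 12.1 does not carry its second-test rule beyond the baseline pair, so the plan is silent on this. Nor do the documents say when the tester sees the VO2peak value.

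It can also be said that section 12.1 defines the endpoint by reference to Table 1, whose CPET entry mentions test acceptability. That entry cites it only as a ground for ending a test, and the criteria themselves are written for baseline. Appendix H (Exercise Physiology Guidelines) is listed but was not available, so a retest rule there cannot be excluded. The CPET, endpoint and analysis sections do not point to it for one.

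None of this supplies a trigger for a Week 17 repeat or says which value is analysed.

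**Conclusion.** The gap is real. Unblinded staff may repeat the primary Week 17 test without a stated reason, and the analysis does not say which value counts. This is an opportunity for selective retesting. The documents do not show that it occurs or in which direction.

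Under the one-arm assumptions above, the A-B shift is about 0.01 to 0.13 mL/kg/min (second test counts) or 0.03 to 0.25 (better test counts) if only the MSK participants are exposed. It is 0.04 to 0.40 or 0.08 to 0.76 if all 58 in Arm B were. These ranges depend on an assumed test-retest SD and assumed repeat rates. Rare or balanced repeats would make the effect negligible. It is a cheap improvement of low-to-moderate priority.

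**What to change.** For the CPET, replace the discretion in sections 10.0 and 10.3 with wording such as:

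*After randomisation, the Week 17 CPET is repeated only if the first attempt meets none of the section 6.2 acceptability criteria, or is lost or stopped for a documented technical or safety reason, decided without reference to VO2peak. The first acceptable Week 17 test is analysed. All repeats and their reasons are logged and reported by arm.*

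State the same first-acceptable-test rule in section 14.3 and apply it to all participants, including any repeats at Duke, where the data allow. For the other endpoints, log repeats by arm and analyse the first technically adequate result. The documents give no adequacy criteria for echocardiography, flow-mediated dilatation, pulse wave velocity or DEXA, so these would need a short definition.

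The cost is a brief amendment, with no added procedure and no change to sample size or power. Investigators lose the latitude to retest a valid test that they think unrepresentative. The trigger also keeps some subjectivity, because one section 6.2 criterion is perceived exertion recorded in an unblinded test.

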10.1 Cardiopulmonary Exercise Testing (CPET)

The midpoint CPET will take the place of one aerobic training session during Week 8 for participants in Arm B. This test is repeated at this time point to re-assess VO_{2peak} under the expectation that VO_{2peak} is likely to have changed in the first 8 weeks of the aerobic training program. Thus, information from midpoint testing is used to re-prescribe the aerobic training prescription to ensure continual physiological adaptations across the entire study period.

This test will not be repeated in the linear aerobic training prescription group (Arm A) or the progressive stretching group (Arm C) at Week 8.

10.2 Fasting Blood Draws

At Weeks 4, 8, and 12, participants will undergo a fasting blood draw to obtain peripheral blood to assess complete blood count (CBC) and secondary endpoints. At Baseline and Study Follow-Up, participants will also undergo fasting blood draws for complete blood count (CBC), lipid panel, fasting glucose, as well as secondary endpoints. The CBC, fasting glucose, and lipid panel will be resulted by MSK clinical labs. Blood for secondary endpoints will be collected under protocol #06-107. Plasma from these research draws will be processed and stored per the Lab Manual, before shipment to a biorepository facility, Kryocal (d/b/a Kryosphere), for long-term banking.

10.3 Exercise Contamination

We will monitor the amount of exercise performed outside of the study in all study arms using subjective methods. Participants in all arms will be asked to complete the GLTEQ at midpoint and at study follow-up to report all exercise behavior performed outside the context of the exercise prescribed in the trial. This questionnaire is important to assess the degree of exercise being performed outside of the structured sessions in all arms, which may potentially contaminate study results. At the midpoint assessment, participants will be asked to report the average weekly exercise performed outside of study aerobic training sessions since study enrollment. At the follow-up visit, participants will be asked to report the average weekly exercise performed outside of study aerobic training sessions over the past 8 weeks since the midpoint assessment.

At the investigators discretion, patients may be required to repeat any of the above assessments.

Table 2. Schedule of Activities

Study Period or Visit Study Week Window (Weeks)	Training begins at Week 1 Treatment Period (16 weeks)						Training ends at Week 17
	Screening	Baseline	Pre-Treatment	Monthly Follow-up	Midpoint Assessment	Monthly Follow-up	Study FU
	NA	-30 days ¹	-2 to -1	4	8	12	17
	NA	NA	±1	±1	±1	±1	±2
General Activities¹							
Informed Consent		X					
Medical History	X						
Height, Weight, BMI	X	X					X
Vital Signs	X						X
Performance Status (ECOG) ²	X						
Concomitant Medications	X						
Randomization ³			X				
Study-Related End Points							
Cardiopulmonary exercise test (CPET) ⁴		X			X ⁵		X
Resting 3D Echocardiogram		X					X
Post-exercise 2D Echocardiogram		X					X
Pulmonary function		X					X
Body composition (DEXA)		X					X
Regional arterial stiffness		X					X
Flow-mediated dilatation (FMD)		X					X
Godin Leisure-Time Exercise Questionnaire (GLTEQ)		X			X		X
Patient-reported outcomes (Lifestyle Questionnaire)		X					X
Complete Blood Count (CBC)		X		X	X	X	X
Lipid Panel & Fasting Glucose		X					X
Aerobic Training ⁶				X	X	X	
Research Blood draw		X		X	X	X	X

- [1] Testing slots/procedures availability must be taken into consideration when scheduling study follow-up visits. Visits may be split across the window to permit for completion of all study-related assessments.
- [2] Performance status by Eastern Cooperative Oncology Group (ECOG) scoring.
- [3] Randomization should be performed on or up to 2 weeks prior to Day 1, but only after eligibility is confirmed.
- [4] All potential participants will perform a second CPET at baseline within 30 days of registration to account for the presence of significant, and potentially clinically important, variability in CPET procedures (VO_{2peak} measurement).
- [5] CPET at Week 8 is only for those randomized to Arm B.
- [6] Arms A and B only [7] Baseline assessments to be completed within 30 days of registration.

11.0 TOXICITIES/SIDE EFFECTS

Toxicity grading will be performed in accordance with NCI CTCAE, v 4.03. Adverse clinical symptoms that occur during or immediately following intervention sessions — with the exception of the expected heart rate, blood pressure, and SpO₂ changes that are related to exercise — will be reported as adverse events. Adverse events will be reviewed by the exercise physiologist, and graded and attributed accordingly at the end of each session. Adverse events that are not resolved at the end of a session will be reviewed with the patient during the next scheduled session to assess whether or not the event is still ongoing. During the intervention phase, adverse events requiring adjustments to the two study aerobic training prescription approaches will be made according to the Ex-Onc Exercise Physiology standards of care and/or at the discretion of the Program Director.

11.1 Side Effects

Anticipated (expected) side-effects associated with a symptom-limited CPET, the two aerobic training doses, or progressive stretching include:

- Fatigue
- Myalgia
- Arthralgia
- Back pain
- Shortness of breath (dyspnea)

Unanticipated but possible side-effects that are *rare, but serious* include:

- Cardiovascular: angina, hypotension, palpitations, rebound hypertension, syncope
- Arrhythmias
- Heart attack
- Stroke

12.1 CRITERIA FOR THERAPEUTIC RESPONSE/OUTCOME ASSESSMENT

12.1 Primary Study End Point

Exercise Capacity (VO_{2peak}): As described in Table 1, VO_{2peak} will be evaluated using an electronic motorized treadmill CPET test with 12-lead ECG monitoring (Mac ® 5000, GE Healthcare).

Due to the presence of significant, and potentially clinically important, variability in CPET procedures (VO_{2peak} measurement), all potential participants will perform a second CPET at baseline to account for potential learning effects and variability.³⁵ If both the first and second CPET achieve acceptable test criteria, results of the second test will be used in all protocol procedures and statistical analyses.

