Patient-reported outcomes (via Lifestyle Questionnaire, Appendix A)	
Patient-reported outcomes will be assessed using a patient-administered questionnaire to assess quality of life, fatigue, pain, and sleep quality.
 
 • Quality of Life (QOL) will be assessed by the Functional Assessment of Cancer Therapy–Breast (FACT-B) scale developed for the assessment of patient symptoms and QOL in breast cancer patients.³⁸ • Fatigue will be assessed using the 13-item FACIT-Fatigue scale for the assessment of fatigue in cancer patients.³⁹ • Pain will be assessed using the 10-item Brief Pain Inventory (BPI) which was designed to measure multiple clinically relevant aspects of pain such as pain intensity and interference from pain in cancer populations.⁴⁰ • Sleep Quality will be assessed by the Pittsburgh Sleep Quality Index (PSQI).⁴¹ • Medical Outcomes Trust Short Form Health Survey (SF-36): The SF-36 is a psychometrically robust self-report questionnaire that measures general health-related quality of life in 8 domains of health: physical functioning (SF-36 PF), role limitations caused by physical health (role-physical), bodily pain, general health perceptions, vitality, social functioning, role limitation due to emotional problems (role-emotional) and mental

	health. ⁴²
Complete Blood Count (CBC), Glucose and Lipid Panel	Blood will be drawn per clinical practice and analyzed by MSK Clinical Chemistry.
Fasting research blood draw	Blood collection should take place prior to the initiation of any-study related interventions, whenever possible.

Following the completion of all baseline assessments and final confirmation of eligibility, participants will be randomized to one of the three study arms.

Participants who do not meet eligibility criteria will be informed of their status and considered a screen failure.

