14.3 Primary and Secondary End Point Analyses

14.3.1 Primary End Point Analysis: The primary objective will be to compare the effects of supervised linear aerobic training (Arm A) versus supervised nonlinear aerobic training (Arm B), relative to progressive stretching (attention-control group) (Arm C), on VO_{2peak} in women with operable breast cancer following the completion of primary adjuvant therapy.

An intent-to-treat statistical analysis will be conducted. Baseline characteristics will be compared using the Fisher exact test for categorical variables or a Wilcoxon rank sum test for continuous variables. The primary end point comparison will be analyzed using a multiple regression model to test for differences among and between the study arms in VO_{2peak} from baseline to the follow-up assessment (Week 17). The regression model will include the stratification factors [i.e., treatment with chemotherapy (yes vs. no) and current treatment with endocrine therapy (yes vs. no)].

In the absence of evidence to the contrary, multiple imputation strategies for missing Week 17 VO_{2peak} data will be performed assuming data were missing at random using logistic regression. Results will be aggregated over 20 imputed sets using the variance formula by Rubin. In addition, a per-protocol analysis will be performed using a multiple regression model to test for differences among and between the study arms in VO_{2peak} from baseline to the follow-up assessment (Week 17) on the basis of exercise adherence to the supervised aerobic training sessions (<80% versus ≥80%). In the event that groups are unbalanced on medical or demographic characteristics at baseline, we will also perform a sensitivity analysis that includes these factors in the model.

14.3.2 Secondary End Point Analyses: As for the primary end point, the intention-to-treat principle will be employed for analysis of all secondary end points. Multiple regression models will be used to test for differences among and between the study arms in secondary end points from baseline to the follow-up assessment (Week 17). The regression model will include the baseline value of the end point, as well as any other baseline characteristics that are not balanced between groups. All secondary end points are continuous.

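### Using both acceptable baseline CPETs as covariate information would add some precision to the primary comparison at little cost; the second-test rule is valid as it stands

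*Combined protocol and SAP*

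**What the plan says.** Section 12.1 gives the reason for two baseline tests as "Due to the presence of significant, and potentially clinically important, variability in CPET procedures", and says that "all potential participants will perform a second CPET at baseline to account for potential learning effects and variability". It then sets the rule for the case where both tests are acceptable: "results of the second test will be used in all protocol procedures and statistical analyses". Footnote 4 to Table 2 repeats the requirement: "All potential participants will perform a second CPET at baseline within 30 days of registration". Section 8.2 fixes the order of events: "Following the completion of all baseline assessments and final confirmation of eligibility, participants will be randomized to one of the three study arms". Section 15.3 agrees that randomization comes after the baseline assessments.

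For the primary analysis, section 14.3.1 describes a multiple regression for VO2peak from baseline to Week 17 and says "The regression model will include the stratification factors", meaning prior chemotherapy and current endocrine therapy. No baseline VO2peak term is listed. For the secondary end points, section 14.3.2 does list one: "The regression model will include the baseline value of the end point".

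**The concern.** The protocol gives two reasons for the second test, learning and variability. Taking the second result deals with learning. It does nothing for variability, because the analysed baseline is still one measurement. If the primary outcome is a change score with no baseline covariate, the whole error of that measurement goes into the outcome.

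A versus B is where precision matters most. Section 14.2 gives it 86% power, against more than 99% for B versus C, and that 86% needs 58 evaluable women in each arm. The first test is already scheduled for every woman, so using it requires no further visit.

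**Working it through.** **Inputs from section 14.2.** 58 per arm; expected changes +1.5 (A) and +4.0 (B), so a difference of 2.5 mL/kg/min; SD of change 4.0; two-sided alpha 0.025.

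**Assumptions, not in the documents.** Retest SD s = 1.0 to 2.0 (0.5 as a low check); between-person SD b = 4.5 to 6; SD of individual learning l = 0 to 1.5.

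**Step 1: the plan's figure.** SE = 4.0 × √(2/58) = 0.743 and 2.5/0.743 = 3.37. The noncentral t gives 86.2% on 114 df, or 86.4% on the pooled 171 df used below. The stated 86% reproduces.

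**Step 2: bias.** Both tests precede randomization, so a learning shift is the same across arms in expectation and is absorbed by the intercept and slopes. Simulations (4,000 trials per scenario) used mean learning of 1 or 3, learning SD 1.0 to 1.5, and eligibility selection on the first test. With both tests as covariates, the A-versus-B estimate averaged 2.49 to 2.51 for a true 2.5.

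**Step 3: precision.** Let the first test be T + learning + error, the second T + error, and Week 17 the true follow-up value + error, always with SD(Week 17 − second test) = 4.0. Write P = 1/(1/b² + 1/s² + 1/(s² + l²)), k = b² + s² and c = k − 8.

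- Case I, true change unrelated to baseline. Residual variance is 16 − s² + b²s²/k with the second test only, and 16 − s² + P with both.
- Case II, equal true-score variance at baseline and Week 17. Residual variance is 16 − 64/k with the second test only, and k − (c/b²)²(b² − P) with both.

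Example, Case I with b = 6, s = 2, l = 0: second test only, 16 − 4 + 144/40 = 15.60; both, 12 + 1/(1/36 + 1/4 + 1/4) = 13.89. The cut is 10.9%.

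| Case | b | s | l | Second only | Both | Cut | A-vs-B power |
|---|---|---|---|---|---|---|---|
| I | 4.5 | 1.0 | 1.5 | 15.95 | 15.74 | 1.4% | 86.5% → 87.0% |
| I | 4.5 | 1.0 | 0 | 15.95 | 15.49 | 2.9% | 86.5% → 87.6% |
| I | 4.5 | 2.0 | 0 | 15.34 | 13.82 | 9.9% | 87.9% → 91.2% |
| I | 6 | 2.0 | 0 | 15.60 | 13.89 | 10.9% | 87.3% → 91.0% |
| II | 4.5 | 1.0 | 1.5 | 12.99 | 12.90 | 0.7% | 92.9% → 93.1% |
| II | 4.5 | 2.0 | 0 | 13.36 | 12.38 | 7.3% | 92.1% → 94.0% |
| II | 6 | 2.0 | 0 | 14.40 | 13.05 | 9.4% | 90.0% → 92.8% |

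The cut runs from 0.7% to 10.9% and the power gain from about 0.2 to 3.7 points. At s = 0.5 the cut is below 1% (Case I, b = 6, l = 0: 16.00 to 15.87, 0.8%). The second test alone as a covariate gives about 86.5% (Case I, b = 6, s = 1.0) to 93%, against 86.4% for the unadjusted change score.

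**Step 4: the mean as a single covariate.** The mean of two tests has error variance (2s² + l²)/4, against s² for the second test alone. With l = 0 it matches the table. It helps whenever l² < 2s². At s = 1.0 and l = 1.5 it is marginally worse, (2 + 2.25)/4 = 1.06 against 1.00, and residual variance rises by at most 0.4%. At s = 0.5 and l = 1.5 it rises by up to 2.7%, about 1 point of power.

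**The case against.** The strongest reply is that nothing here is wrong. The second-test rule is pre-specified and reasoned. Treating the first test as familiarization is coherent, and the randomized contrast is valid under it. That stands. A reader might infer that the primary analysis is biased or the 86% miscalculated; the documents support neither.

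A second reply is that using the first test brings the learning effect back. That would hold for a before-after change within one arm. It does not hold for contrasts between arms when both tests precede randomization.

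A third reply is that the gain cannot be sized. That largely stands. It is tempting to promise a narrow variance saving or a number of women saved per arm, but with no retest SD in the documents only a wide range is supportable. It is also tempting to take power from a change score based on the mean of two tests: variance 16 − s²/2 gives SD 3.94 to 3.74 for s = 1.0 to 2.0, and power 87.3% to 90.6% on 114 df. Those figures belong to a different analysis from the covariate model.

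Finally, much of the benefit may come from including any baseline VO2peak covariate. That stands too, and section 14.3.1 currently lists none.

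**Conclusion.** An optional but worthwhile refinement. The first acceptable test has no analytic role, and it can be given one without bias to the arm contrasts. Relative to a model already adjusted for the second test, the gain is about 1% to 11% of residual variance, or about 0.2 to 4 points of A-versus-B power, under the assumed SDs and the planned SD of change of 4.0. It is close to nil if retest error is small.

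Two things could shrink it. Learning that varies widely between women makes the first test less informative. The documents also do not say whether the 115 women randomized at the first site, 66% of 174, had two acceptable tests. Using both tests would not remove any practice effect from the Week 8 CPET, which only Arm B performs.

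**What to change.** Leave the second test in place for all protocol procedures. In sections 12.1 and 14.3.1, state before any outcome data by arm are seen that Week 17 VO2peak is regressed on:

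- arm;
- the two stratification factors;
- the mean of the acceptable baseline CPET values, or the single value where only one is acceptable;
- an indicator for one versus two acceptable tests.

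If the team expects learning to vary between women by more than Step 4 allows (l² above 2s²), it can add the difference between the two tests, set to zero where there is only one. For women with two tests this is equivalent to entering both values separately. The plan should name one form and not leave the choice open.

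The cost is a short edit in each section and two or three degrees of freedom out of about 170, with no new data collection. The team should first count how many first-site women have two acceptable baseline tests, since that decides how much there is to gain. If few do, adding the second-test value as a baseline covariate is the part to keep.
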